3.3 Inclusion of Women and Minorities

Both men and women and members of all ethnic groups are eligible for this trial.

3.4 Study Duration and Dates

The study will commence in Winter, 2014 and should meet accrual by Autumn, 2015, assuming approximately two accruals per month. These are estimates only. Of note, should a patient be found to exhibit stable or improved disease after completing 6 cycles, a consideration will be given to continuing maintenance treatment of decitabine, but this will be optional and not part of this protocol.

3.5 Prior and concomitant medications

Patients may not have had prior exposure to decitabine, rapamycin, or ribavirin. No other investigational agent may have been received within two weeks, but otherwise there are no exclusions on numbers and types of prior therapies for AML. As discussed below, hydroxyurea and/or leukapheresis may be utilized for control of circulating blast count at the inception of cycle 1 and 10 days into the cycle.

4.0 TREATMENT PLAN

4.1 Agent Administration

Treatment will be administered on an outpatient basis whenever possible. Reported adverse events and potential risks for decitabine, rapamycin, and ribavirin are described in Section 5. No investigational or commercial agents or therapies other than those described below may be administered with the intent to treat the patient's malignancy.

ULEU-13049 13 Version date: 09Aug2017

4.1.1 Study schema

Note: Those patients with morphologic M4/M5 subtypes²⁸ will be treated on Arm B and all other subtypes on Arm A. At study entry, all patients will have samples procured for testing of eIF4E expression but this will not determine allocation to arm A or B which will be made solely on the basis of FAB subtype. M4 subtype is acute myelomonocytic leukemia and M5 acute monocytic leukemia.

- Decitabine (Arms A and B)
- 20mg/m2 will be given as an intravenous infusion daily for 10 consecutive days starting on day 1 of cycle 1.
- In subsequent cycles, decitabine will be given for 5 days (day 1-5)

Rapamycin (Arm A)

- o For non-M4/M5 AML cases²⁸
- A 6 mg loading dose will be administered on Day 11 in cycle 1 and day 6 in subsequent cycles. Thereafter, 2 mg/day will be administered per schedule below. This may be reduced to 1 mg/day if levels are elevated (>15 ng/mL).
- o Toxicities will be as defined in section 9 using NCI Common Toxicity Criteria for Adverse Events (CTCAE (version 4.0) Appendix 3)
- o Rapamycin will be given from day 11 to 22 in cycle 1 and on days 6 to 22 in subsequent cycles.

Dose Level	Rapamycin	Decitabine
Level -1	1 mg	20 mg/m2
Level 1	2 mg	20 mg/m2

The rapamycin dose for phase II of the study was chosen based on results from the phase I study (ULEU08049).

Ribavirin (Arm B)

For M4/M5 cases²⁸—These patient are anticipated to have high eIF4E expression as expressed by Western blotting²⁴.

In cycle 1, ribavirin will be dosed from Day 11 through Day 28.

In subsequent cycles, ribavirin will be started on Day 1 on a continuous basis until study completion. These doses were chosen based on those found effective and tolerated in previous studies²⁴.

Dose level cohorts are listed in the table below. Subject enrollment will start at **Dose Level 1** (1000 mg). Enrollment in subsequent dose levels (escalation to Dose level 2 and 3, or de-escalation to Level -1 and -2) will follow the dose escalation and dose de-escalation plans as outlined below.

ULEU-13049 14 Version date: 09Aug2017

Dose Level	Ribavirin	Decitabine	Description
Level -2	600 mg bid	20mg/m2	Dose de-escalation cohort
Level -1	800 mg bid	20mg/m2	Dose de-escalation cohort
Level 1	1000 mg bid	20mg/m2	Initial cohort
Level 2	1200 mg bid	20 mg/m2	Dose escalation cohort
Level 3	1400 mg bid	20mg/m2	Dose escalation cohort

Dose Escalation Plans for Ribavirin (Arm B)

Number of patients with DLT at a given dose level	Escalation Decision Rule
0 out of 3	Enter 3 patients at the next dose level
≥ 2	Dose escalation will be stopped. This dose level will be declared the maximally administered dose (highest dose administered). Three (3) additional patients will be entered at the next lowest level if only 3 patients were treated previously at that dose.
1 out of 3	Enter at least 3 more patients at this dose level. – If 0 of these 3 patients experience DLT, proceed to the next dose level. -If 1 or more of this group suffer DLT, then dose escalation is stopped, and this dose is declared the maximally administered dose. Three (3) additional patients will be entered at the next lowest dose level if only 3 patients were treated previously at that dose.
≤ 1 out of 6 at highest dose level below the maximally administered dose	This is generally the recommended phase 2 dose. 6 patients must be entered at the recommended phase 2 dose before going to Phase 2.

An ad hoc confidential person will ensure that no unexpected adverse events have occurred at each dose level before enrollment on the next dose level commences. This will be handled through the DSMB of the James P Wilmot Cancer Center. THIS WILL REQUIRE THAT THE LAST PERSON ENROLLED AT THE PRIOR COHORT HAS BEEN FOLLOWED FOR 30 DAYS FROM THE START OF THERAPY.

Dose De-escalation: If 1000 mg bid proves to be the MTD, a cohort at 800 mg bid will be treated, and if that is too toxic, one at 600 mg bid will be enrolled (level -2). No further dose de-escalation would be planned. Safety assessment at each cohort would be as indicated above.

4.1.1.1

Cycle Duration

Cycles will begin on an every 28 day basis which may be extended to 30 days to account for weekends, holidays, logistics of marrow aspirate and biopsy scheduling.

Routine Clinical Monitoring.

Routine CBC with differential and platelets as well as a comprehensive metabolic profile including renal and hepatic function will be evaluated on a twice weekly basis and more frequently as cytopenias or metabolic abnormalities indicate. For those patients receiving rapamycin, a trough Rapamycin level will be performed at day 14 and 21 of each cycle.

Marrow Status Monitoring.

Marrow aspirate only will be obtained after the first ten days (on days 10 or 11) of decitabine in the first cycle. At the end of the first cycle and third cycle or at the time of full peripheral blood count recovery, whichever comes first, a bone marrow aspirate and biopsy will also be obtained. Marrow may be obtained between days 22 and 26 of the 1st and 3rd cycles, and a marrow at time of withdrawal from study is recommended but is optional.

Number of Cycles.

If there is no overt progression of disease (defined as doubling of the peripheral blood blast count) after the first cycle, the patient will proceed on study and receive two more cycles. If after the third cycle there is evidence of a PR/CR or stable disease, the patient will remain on study for 3 more cycles. The maximum number of cycles that each patient may receive is six. As noted above, physicians may use maintenance decitabine, but this will be off protocol.

Long Term Follow Up

Patients will be followed for survival status every 6 months for up to 2 years after last date of treatment.

4.1.2 Informed Consent

Prior to any study procedures being performed, written informed consent must be obtained for each patient. Each patient will sign the IRB approved informed consent, and the patient will be given a copy of the signed and dated consent. The original signed version will be retained in study files in the Clinical Trials Office of the University of Rochester Cancer Center. Information on all patients screened for the trial will be recorded with indication of reasons for non-participation or non-eligibility. All information will be stored in a secure place.

ULEU-13049 16 Version date: 09Aug2017

4.1.3 Registration

To register a patient, the eligibility checklist and consent form will be sent to the research nurse or data manager who will then register the patient. The Clinical Trials Office of the University of Rochester Cancer Center will register all patients by phoning [contact]. The PI will sign each registration form which will include inclusion and exclusion criteria.

4.2 Supportive Care Guidelines

4.2.1 Blood Transfusion: Transfusion Parameters:

 $Hb \le 7$ mg/dl or HCT <21 % in the absence of cardiopulmonary disease inpatient and <24% outpatient.

HCT <27 % in presence of cardiopulmonary disease.

4.2.2 Platelet Transfusion: Transfusion Parameters:

Active Bleeding OR

Platelets <10,000/μL inpatient or <15,000/μL outpatient. OR

Platelets $< 20,000/\mu L$ in the presence of infection or fever.

4.2.3. Infectious Disease Prophylaxis

- 4.2.3.1 Antibiotics: Ciproflaxcin 500mg po BID or moxifloxacin 400 mg/day may be used during times of neutropenia at the discretion of the treating physician.
- 4.2.3.2 Antivirals: Acyclovir, Valacyclovir, or Famciclovir are permitted.
- 4.2.3.3 Antifungals: Fluconazole 200mg QD prophylaxis if patient is neutropenic until ANC >500/uL. Dosage should be adjusted according to liver function. Voriconazole and posaconazole may result in elevated sirolimus levels and should be utilized with caution and only in the case of documented fungal infections. Their use is permitted for those on Arm B.
- 4.2.3.4 Anti-Emetics: Use of anti-emetics will be at the discretion of the treating physician.

4.2.4 Tumor-lysis prophylaxis

- 4.2.4.1 Allopurinol 300 mg/day po on day -1 or 0 until day 14 or WBC < 500/ul. Rasburicase may be utilized for extreme uric acid elevations per institutional standards of care
- 4.2.5 Graft vs. Host Disease Management—See also 4.3.4. For those patients who are S/P allografting and who have a flare of GVHD during therapy, this can be treated at the investigators' discretion with steroids, mycophenylate mofetil, or photopheresis. If a

calcineurin inhibitor is required, a patient on Arm A would need to be removed from trial based on potential interaction with Rapamycin.

Other supportive care will be per institutional standards of care. This will include treatment of neutropenic fever, management of bleeding, nausea, mucositis, or other toxicities. Neupogen will not be utilized routinely but may be used in settings of infection or fever at the treating physicians' discretion.

4.3 Concomitant Therapy

4.3.1 In general, concomitant medications and therapies deemed necessary for the supportive care and safety of the patient are allowed provided their use is documented in the patient record and on the appropriate case report form. The administration of any other systemic anticancer agents including chemotherapy, radiation therapy or biologic agents including donor leukocyte infusions is **NOT** permitted. Similarly, concurrent use of other investigational agents or their use in the 28 days prior to enrollment is not allowed.

For any patient with a WBC greater than 50,000, consideration will be given for pretreatment with an appropriate dose of hydroxyurea to cytoreduce prior to the first dose of decitabine. Decitabine will not be started until the absolute blast count is less than 15,000/uL. Hydroxyurea may be continued into the first cycle until appropriate cytoreduction has occurred and should then be discontinued. In extreme cases of WBC elevation or in the presence of hyperleukostasis symptoms, leukapheresis may be employed for cytoreduction along with hydroxyurea.

For those patients who relapse after allogeneic transplant, tacrolimus/cyclosporine or steroids should be tapered off if no GVHD occurs. If GVHD occurs/progresses during therapy, it should be treated initially with steroids. Calcineurin inhibitors should be avoided. Mycophenylate mofetil may be utilized. See also 4.2.5.

4.4 Dose Calculation

Dose of decitabine will be based on body surface area calculated on actual body weight. No correction for obesity will be made. The dose of rapamycin or ribavirin is a fixed, non-calculated dose.

4.5 Dose Modification

4.5.1 Rapamycin

4.5.1.1 Dose modifications for non-hematological toxicity

Grade 2 (in accordance with the NCI CTCAE version 4.0)

If the patient experiences a Grade 2 non-hematologic toxicity, study drug must be withheld until the toxicity has resolved to less than or equal to Grade 1. Rapamycin may then be resumed at the 2 mg daily dose. If the grade 2 toxicity recurs, Rapamycin must be withheld until the toxicity has resolved to less than or equal to Grade 1. In those patients receiving 2 mg/day, dosing will be restarted on a 1 mg/day basis. If this recurs at the 1 mg dosing, rapamycin can then be dosed at 1 mg/ qod, but this is the lowest dose allowed.

Grade 3 or 4

If a patient experiences a Grade 3 or 4 toxicity, study drug must be withheld until the toxicity has resolved to less than or equal to grade 1 and the daily dose must be reduced to 1 mg/day from 2 mg per day, If the Grade 3 or 4 toxicity recurs, Rapamycin must be withheld until the toxicity has resolved to less than or equal to Grade 1, and the daily dose must be reduced to 1 mg qod. If the same toxicity occurs again, the drug must be stopped.

4.5.1.2 Dose modifications for hematologic toxicity

Grade 2

No dose interruptions will be performed for grade 1 or 2 hematologic toxicity because it is anticipated that all patients may become pancyopenic as a result of treatment or from the AML itself.

Grade 3 or 4

No dose reductions will be performed for grade 3 or 4 anemia, neutropenia and thrombocytopenia. Patients will receive supportive care as specified in section 4.2. Cycles may be delayed up to a week in the event of stable disease if severe neutropenia and/or active infection are present until the infection is controlled and neutropenia stabilized or improving.

Dose modifications for other reasons

If vomiting occurs following rapamycin administration, an extra dose will not be given that day and antiemetics will be prescribed to enable resumption of the next day's dose.

Grade 3 infections, fatigue, weight loss, and electrolyte imbalances are anticipated in relapsed AML patients and will be appropriately treated but are not deemed study related toxicities and will not result in dose modifications.

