2.4 Rapamycin

Rapamycin is a macrolide fungicide isolated from the bacteria Streptomyces hygroscopicus with potent antimicrobial, immunosuppressant and antitumor activities and is approved for the prevention of allograft rejection following organ transplantation. Rapamycin binds to the immunophilin FK506 binding protein 12 (FKBP12) and forms a complex which then binds to mTOR and inhibits downstream signaling events. The sensitivity of various AML cell lines to increasing concentrations of rapamycin in clonogenic assays has been measured. There appears to be a variable degree of sensitivity with UT-7EPO and UT-7GM cell lines being insensitive, K562, U937, HEL and HL60 being moderately sensitive and the immature KG1 and KG1a cell lines being strongly inhibited by low concentrations of rapamycin. Nine patients with relapsed, refractory or poor-risk AML were treated with rapamycin as a single agent, with a partial response (> 50% reduction in the absolute number of blasts or at least a 50% reduction in the percentage of marrow blasts) occurring in 4 patients. 4 patients had progressive disease and one had stable disease. ²² As a single agent, rapamycin has had minimal activity in AML. Rapamycin has been combined with cytototoxic chemotherapy in newly

ULEU-13049 10 Version date: 09Aug2017

diagnosed patients in early phase trials²³ with no positive effects on CR rates noted. Rapamycin has also been utilized in the therapy of ALL, and it is also used after allogeneic stem cell transplantation for prophylaxis of graft vs. host disease in combination with tacrolimus or methotrexate.

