4.5.3.2 Dose Modifications for non-hematologic toxicity

For non-hematologic toxicities thought due to ribavirin, the drug will be held until toxicity resolves to less than or equal to grade 1. If the resumption of ribavirin results in the same toxicity, dose will be lowered by one cohort, and for those on 1000 bid, dose may be reduced to 800 mg bid (dose level -1). If toxicity occurs at that level, ribavirin will be redosed at 600 mg bid (dose level -2), and if toxicity occurs at that dose, ribavirin will be stopped.

ULEU-13049 20 Version date: 09Aug2017

Grade 3 infections, fatigue, weight loss, and electrolyte imbalances are anticipated in relapsed AML patients and will be appropriately treated but are not deemed study related toxicities and will not result in dose modifications

4.5.4 Other dose modifications according to standard clinical practices are to the discretion of the treating physician. The study coordinator and primary investigator (s) should be notified of such modifications. As examples, treatment can be delayed at the discretion of the investigator for disease-related complications such as febrile neutropenia, infection, mucositis, hemorrhage, or extreme fatigue and debility.

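### For infections, fatigue, weight loss and electrolyte imbalances, Arm A requires a rapamycin hold at grade 2 but none at grade 3; in Arm B the same reversal affects only events attributed to ribavirin

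*Combined protocol and SAP*

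**What the plan says.** **Arm A (rapamycin).** The schedule in section 4.1.1 is "Rapamycin will be given from day 11 to 22 in cycle 1 and on days 6 to 22 in subsequent cycles", with a 6 mg loading dose and then 2 mg daily. Section 4.5.1.1 sets the rule for non-hematologic toxicity:

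- At grade 2: "If the patient experiences a Grade 2 non-hematologic toxicity, study drug must be withheld" until it has settled to grade 1 or lower. The drug restarts at 2 mg; a recurrence leads to a second hold and a restart at 1 mg daily. There is no condition on cause, and no category is left out.
- At grade 3 or 4: "If a patient experiences a Grade 3 or 4 toxicity, study drug must be withheld", followed by a reduction to 1 mg daily.

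Section 4.5.1.2, under dose modifications for other reasons, makes an exception: "Grade 3 infections, fatigue, weight loss, and electrolyte imbalances are anticipated in relapsed AML patients". These events are to be treated but "are not deemed study related toxicities and will not result in dose modifications". The exception names grade 3 only.

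**Arm B (ribavirin).** Section 4.5.3.2 conditions its rule on cause: "For non-hematologic toxicities thought due to ribavirin, the drug will be held until toxicity resolves to less than or equal to grade 1". The same grade 3 exception follows it.

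**Both arms.** Section 4.5.4 adds: "Other dose modifications according to standard clinical practices are to the discretion of the treating physician". Its examples of complications that can justify a delay include infection and extreme fatigue.

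**The concern.** A mandatory safety rule should be at least as strict at grade 3 as at grade 2. Taken literally, an Arm A patient with a grade 2 infection must stop rapamycin, while one with a grade 3 infection need not. If the grade 3 infection then improves to grade 2, the hold becomes compulsory at the point of improvement. The plan gives no reason for this order.

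The rule can do harm in either direction:

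- **The event is drug-related.** The exception leaves the sicker patient on drug. This is plausible for infection, since section 2.4 credits rapamycin with "potent antimicrobial, immunosuppressant and antitumor activities". Section 4.2.3.3 also allows voriconazole or posaconazole, with caution, for documented fungal infection and warns that they can raise sirolimus levels. Levels are scheduled only on days 14 and 21.
- **The event comes from the leukemia.** The grade 2 rule takes drug away from a patient in an arm that tests efficacy, and a recurrence halves the daily dose.

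**Working it through.** The plan has no figure of its own on this point, so the check is a comparison of the text followed by a measure of exposure.

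**1. The written rule for the four categories**

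| Grade | Arm A, any cause | Arm B, thought due to ribavirin | Arm B, other cause |
|---|---|---|---|
| 2 | Hold (4.5.1.1) | Hold (4.5.3.2) | No hold |
| 3 | No modification (4.5.1.2) | No modification (4.5.3.2) | No modification |
| 4, where it exists | Hold, then 1 mg/day (4.5.1.1) | Hold (4.5.3.2) | No hold |

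Section 4.5.1.1 deals with holds under a heading about dose modifications, so an instruction not to modify the dose covers holds as well as reductions. Arm A reverses whatever the cause. Arm B reverses only in the attributed column.

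**2. Does a narrower reading of toxicity remove the Arm A reversal?** Suppose toxicity in 4.5.1.1 means drug-related events only. An attributed grade 2 event is then held, and an attributed grade 3 event is still exempt under 4.5.1.2. The reversal remains for attributed events. It disappears for unrelated events only if the site carries the grade 3 convention down to grade 2, which 4.5.1.1 does not say.

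**3. Length of the gap (section 4.1.1; six-cycle maximum)**

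- Cycle 1: days 11 to 22 = 12 days; 6 + 11 × 2 = 28 mg.
- Cycles 2 to 6: days 6 to 22 = 17 days each; 6 + 16 × 2 = 38 mg.
- Maximum: 12 + 5 × 17 = 97 dosing days.

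A grade 3 event in these categories carries no mandatory stop for what remains of its 12- or 17-day course.

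**4. How often it might matter.** Section 11.0 gives 9 evaluable patients if Arm A stops after stage 1, otherwise 24. The documents give no event rates, so r, the proportion of patients with a drug-attributed grade 3 event in these categories, is an assumption. P(at least one) = 1 − (1 − r)^n:

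| r (assumed) | n = 9 | n = 24 |
|---|---|---|
| 2% | 0.166 | 0.384 |
| 5% | 0.370 | 0.708 |
| 10% | 0.613 | 0.920 |

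These are chances that the gap is met at all. They do not measure harm.

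**The case against.** The strongest reply is that the exception is deliberate. These events are expected in AML, the plan repeats the exception in 4.5.1.2, 4.5.3.2 and 9.4, and patients are not left without cover. Section 4.5.4 names infection and extreme fatigue as reasons for delay. Cycles may be put back by up to a week for active infection in stable disease. A scheduled rapamycin level above 15 ng/mL forces a hold (4.5.1.3). Chemistry is checked twice weekly, and section 15.0 allows discontinuation for unacceptable toxicity. With a mean half-life of 62 hours (5.2), a mid-course hold also lowers exposure only gradually.

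Much of this stands. It shows that protection exists and that no harm has been quantified. It does not repair the rule: 4.5.4 and section 15.0 are discretionary, the cycle delay concerns when a cycle starts, and the level rule responds to drug concentration, not to the event. A half-life of 62 hours is about 2.6 days (62/24), short enough for a hold early in a 12- or 17-day course to matter. Expecting grade 3 events from the disease also does not explain a compulsory hold at grade 2.

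A reader might also infer that 9.4 contradicts itself, so that attributed grade 3 electrolyte events go uncounted and ribavirin escalates too readily. The text does not support that. Its first sentence gives a general test for a dose-limiting toxicity (DLT) based on attribution; its second fixes the attribution of four named grade 3 categories. Read together, those events are not DLTs. Section 5.3.3.4 lists low calcium and low magnesium for ribavirin, but without grade or frequency. Whether to count such events is a design preference.

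**Conclusion.** The point holds for Arm A as written: in four categories the mandatory rapamycin rule runs hold, no modification, then hold and reduce. In Arm B it holds only for events thought due to ribavirin; extending it to all Arm B events would ignore the attribution condition in 4.5.3.2. Nor do the documents support saying that patients are unprotected at grade 3. Protection there rests on the physician's judgment, where at grade 2 it rests on a rule.

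The text comparison needs no assumption. The size does: the length of the gap follows from the schedule, but the chance of meeting it ranges from 0.17 to 0.92 over assumed rates of 2% to 10% and the two possible sizes of Arm A. No effect on the response test or its two-stage boundaries has been shown. This is a real inconsistency in a safety instruction, cheap to correct and partly mitigated by discretion.

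**What to change.** - **4.5.1.2 and 4.5.3.2:** limit the exception to grade 3 events in the four categories that are judged unrelated to study drug. Attributed grade 3 events then follow the existing rules: hold and reduce to 1 mg daily in Arm A, hold in Arm B.
- **4.5.1.1:** exempt grade 2 events in the same four categories when judged unrelated. Leave the rest of the grade 2 rule as it is.
- **9.4:** leave the DLT rule unchanged. At most, add that grade 3 events in the four categories are not DLTs and that dosing follows 4.5.3.2. Do not insert the relatedness condition here, because that would turn attributed grade 3 events in all four categories into DLTs.

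After these changes, Arm A reads hold, hold and reduce, hold and reduce for attributed events, and no mandatory change at grade 2 or 3 for unrelated ones, with grade 4 as now. Neither sequence reverses.

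The cost is a wording amendment with no new data, since adverse events are already recorded (9.2). There are two downsides: an occasional extra hold or reduction for attributed grade 3 events, and loss of the mandatory hold for unrelated grade 2 events in these four categories. The second removes a current safeguard, so the amendment should say so openly; 4.5.4 would still allow a discretionary hold.
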